**PARTNERS HUMAN RESEARCH COMMITTEE
PROTOCOL SUMMARY**

Answer all questions accurately and completely in order to provide the PHRC with the relevant information to assess the risk-benefit ratio for the study. Do not leave sections blank.

PRINCIPAL/OVERALL INVESTIGATOR

[name]

PROTOCOL TITLE

Treatment of Field Cancerization for Reduction in Tumor Burden – A Prospective Study

NCT NUMBER

NCT02150863

FUNDING

Wellman Center for Photomedicine

VERSION DATE

December 28, 2016

SPECIFIC AIMS

Concisely state the objectives of the study and the hypothesis being tested.

This project aims to treat field cancerization in a manner that will reduce the tumor burden in patients with significant photodamage

1. To demonstrate that we can reduce the non melanoma skin tumor burden over time by treating the entire field of actinic keratoses and atypical keratinocytes.
2. To compare the efficacy and side effects of ablative CO2 laser resurfacing vs. ablative CO2 laser resurfacing plus post treatment suction blister epidermal grafts vs. control (no intervention).
3. To demonstrate a reduction in the number of actinic keratoses over time
4. To demonstrate an improvement in clinical appearance of the treatment area
5. To demonstrate a reduction in the degree of P53 mutations seen with histopathology
6. To demonstrate that subjects tolerate the treatment with few side effects
7. To demonstrate increased telomere length in treated areas

BACKGROUND AND SIGNIFICANCE

Provide a brief paragraph summarizing prior experience important for understanding the proposed study and procedures.

Field cancerization is a risk for any individual with excessive and prolonged sun exposure, immunosuppression, or exposure to radiation or carcinogens. We are very good at treating the skin cancer but if we leave behind the atypical field of keratinocytes it is only a matter of time

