The proposed pilot study is a 3 year prospective, randomized, controlled comparison of a single treatment with carbon dioxide laser resurfacing vs. carbon dioxide resurfacing plus autologous epidermal skin graft from a non sun exposed site vs. control. Thirty subjects will receive treatment with each of the modalities on randomly-assigned portions of the treatment area. The primary measures of efficacy are (a) count of the number of actinic keratosis and non melanoma skin cancers, (b) blinded evaluation of severity from standard digital photographs taken before and after the treatments, and (c) change in histology before and after treatment: seen by grading and change of p53 immunostaining. Other study endpoints include time point to the next skin cancer is found in the treatment area, overall clinical appearance, change in mutant P53 of skin samples, and telomere length variability.

Safety measures include (a) pain, (b) scarring, (c) wound healing, (d) and infection

Subjects will be recruited through advertisements posted within the hospital(s), outpatient dermatology clinics and partners electronic mail.

Inclusion criteria

1. Subjects with ages between 18 and 85 years, male or female.
2. Subjects with at least 4 clinically diagnosed AKs per treatment site (up to 200 sq cm), excluding the face.
3. Subjects with history of at least 1 skin cancer within the past year
4. Willingness to participate in the study
5. Informed consent agreement signed by the subject
6. Willingness to follow the treatment schedule and post treatment care requirements
7. Willingness to not use topical or systemic (oral) TREATMENT medications including imiquimod, 5 Fluorouracil, photodynamic therapy, during the treatment period.
8. Has not had treatment for AKs in the treatment area for 4 weeks prior to enrollment

Exclusion criteria

1. Subjects with active skin cancer in the treatment area. Once the non-melanoma skin cancer has been treated, the subject can be immediately enrolled.
2. Infection of the area to be treated
3. An open wound in the area to be treated
4. Presence of suntan in the area to be treated, or active tanning during the study
5. Subjects who have taken medication known to induce photosensitivity in the previous 3 months
6. The patient has any contraindication to use of the CO2 laser
7. Subject is unable to comply with treatment, home care or follow-up visits
8. Subject is pregnant or breast feeding

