Visit	Informed consent	Urine preg test	TX	Photo	# NMSC prior	AK/NMSC count	Biopsy	Overall Appearance scale	AE	Pain scale (VAS)	Patient side effect report	Inv wound assess
Screen	X											
Baseline/TX (Day 0)		X	X	X	X	X	X	X	X			
Day 3				X				X	X	X	X	X
Day 7				X				X	X	X	X	X
Week 4				X		X		X	X	X	X	X
3 month				X		X	X	X	X			X
6 month				X		X		X	X			
1 year				X		X		X	X			
1.5 – 2.5 year visits				X		X			X			
3 year				X		X	X	X	X			

Baseline/Treatment Visit 1(Day 0)

- Baseline and treatment can occur on separate days if necessary. These visits will occur within 2 weeks of each other if done separately**

Part I– Baseline Evaluations (lasting 1 hour).

Part II- Treatment (lasting 2.5 hours)

Part I– Baseline Evaluations (lasting 1 hour).

The investigator will determine the treatment area

- I. AK count within the treatment area**
- II. Confirm no clinically evident NMSC within the treatment area**
- III. Obtain history of number of skin cancers and locations. History will be taken orally from patient but will also review the medical records.**
- IV. Tracings of the treatment area and control site as needed to document**

V. Shave biopsy technique will be used to harvest epidermal biopsies for histologic assessment. 6 scouting biopsies will be done in the treatment area for histologic evaluation and immunostaining

VI. Baseline pre-treatment Photography of treatment area and control site

Shave biopsy for histology

Area will be prepped with alcohol swab, injected with Lidocaine 1% with or without epinephrine. Shave biopsy will be performed with a dermablade. Tissue samples will be taken to the lab and processed for immunostaining of p53 and PCR to determine telomere length. A portion will be frozen and backed for PCR analysis at the end of the study.

Part II- Treatment (lasting 2.5 hours)

- I) Urine pregnancy test for female not yet in menopause
- II) Subject will receive laser treatment to the treatment area. Topical anesthesia will be applied for 1 hour prior to the laser treatment.
- III) Epidermal suction blister graft harvest from donor site and application on randomized treatment area
- IV) Adverse event evaluation
- V) Patient assessments: pain

Procedures in more detail

Laser treatment

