The laser used is the Ultrapulse CO2 Laser (Lumenis). Patients will be treated according to the standard of care. The settings used for the CO2 laser will be commonly used settings that will ablate down to the bottom layer of the epidermis (8 – 20 J/cm²). Any remaining epidermis will be removed with saline soaked gauze. The papillary dermis has a characteristic glistening appearance and this will also be used as a treatment endpoint. If the papillary dermis is seen, the treatment in that area will be considered completed.

Participants or caregivers will be instructed to do saline soaked gauze soaks three times daily and apply Vaseline™ or Aquaphor™ onto the treated areas for up to 7 days post op as needed. Wound care instructions will be given to the patient, and a Day 3 follow-up visit will be scheduled.

Epidermal Blistering and Micrograft Preparation

A suction device will be applied to area of skin approximately 5.0 cm in diameter. This will be left in place approximately 30-40 minutes and may cause mild discomfort because of the suction. After the microblisters have been raised, the blister roofs (a superficial epidermal sample) with an average thickness of 200 microns and size of 1.75 mm in diameter will be removed and transferred to a sterile Tegaderm wound dressing that will be applied to the recipient site. The superficial donor wound will then covered with sterile Tegaderm or Duoderm.

Post- Procedure follow up Visits (Day 3, Day 7) (lasting 30 minutes)

- I) Photography

- II) Exam of the treatment area: wound check; evidence of scarring, evidence of infection; evidence of healing
- III) Adverse event evaluation
- IV) Investigator assessments: wound assessment, overall clinical appearance
- V) Patient assessments: pain scale and side effects

Follow-up Visits(Week 4) (lasting 30 minutes)

- I) Photography
- II) Exam of the treatment area: AK count, evaluate for clinically appearing NMSC present; evidence of scarring, evidence of infection; evidence of healing. Also will get history from patient: visits to dermatologist? and treatments rendered?.
- III) Adverse event evaluation
- IV) Investigator assessments: wound assessment, overall clinical appearance
- V) Patient assessments: Pain scale and side effects

Follow-up Visits

(Month 3) (lasting 1.5 hours)

- I) Photography

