- II) Exam of the treatment area: AK count, evaluate for clinically appearing NMSC present; evidence of scarring, evidence of infection; evidence of healing . Also will get history from patient: visits to dermatologist? and treatments rendered? Will also review medical records to confirm the history.
- III) 6 scouting epidermal biopsies, using shave biopsy technique (from the treatment area) for histology and immunostaining. Will also bank a portion for PCR at the end of the study.
- IV) Adverse event evaluation
- V) Investigator assessments: wound assessment, overall clinical appearance

Follow-up Visits(6 months, 1 year, 1.5 year, 2 year, 2.5 year) (lasting 30 minutes each)

- I) Photography
- II) Exam of the treatment area: AK count, evaluate for clinically appearing NMSC present; evidence of scarring, evidence of infection; evidence of healing . Also will get history from patient: visits to dermatologist? and treatments rendered? Will also review medical records to confirm the history.
- III) Adverse event evaluation
- IV) Investigator assessments: overall clinical appearance

End of Study visit (3 year) (lasting 1.5 hours)

Patients will exit the study after 3 years

- II) Photography
- III) Exam of the treatment area: AK count, evaluate for clinically appearing NMSC present; evidence of scarring, evidence of infection; evidence of healing . Also will get history from patient: visits to dermatologist? and treatments rendered? Will also review medical records to confirm the history

- IV) **6 scouting epidermal biopsies, using shave biopsy technique (from the treatment area) for histology and immunostaining. Will also bank a portion for PCR at the end of the study.
- V) Adverse event evaluation
- VI) Investigator assessments: overall clinical appearance

** During the course of the study, the subjects will have a total of 18 scouting epidermal biopsies using the shave biopsy technique

Evaluation of Safety and Efficacy

Assessed by investigators (non-blinded) and by blinded evaluators (clinical photographs), periodically for 3 years after a single treatment session.

Reported by the Patients

Specific form is attached.

I. Side effects reported by the patient:

To assess major and minor side-effects, patients will be asked for each treatment site to fill in the following sentence for each test site: **“The side effects I experienced after the treatment were:”** E.G.

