Table I. **N/A:** Did not have this side effect / **1:** Mild / **2:** Moderate / **3:** Severe

A. Blistering	N/A	1	2	3
B. Scarring	N/A	1	2	3
1. Swelling	N/A	1	2	3
2. Redness	N/A	1	2	3
3. Scabs (crusting)	N/A	1	2	3
4. Weeping skin (pustulation)	N/A	1	2	3
5. Scaling or flaking skin (exfoliation)	N/A	1	2	3
6. Itchy skin	N/A	1	2	3
7. Erosion (ulceration)	N/A	1	2	3
8. Tanning	N/A	1	2	3
9. Lightening of the skin	N/A	1	2	3
11. Wheals	N/A	1	2	3
12. Bleeding	N/A	1	2	3
13. Folliculitis/ Acne	N/A	1	2	3
14. Oozing	N/A	1	2	3
15. Change in sensitivity/numbness	N/A	1	2	3

[figure not shown]
I. Pain assessment - Visual Analog Scale (VAS).

The VAS will be completed by study subject immediately after the treatment, and at each procedure follow up visit (Day 3, Day 7, week 4)

Pain is any of the following: sensation of tingling, stinging, prickling, or burning feeling, heat under the skin, tenderness, mild, moderate or severe pain).

Specific VAS form is attached

Patients will be asked to circle the number below that most closely corresponds to pain associated with their DISEASE.

Reported by the Investigators and Blinded-evaluators

Reported by the Investigator

Specific form is attached.

Investigator's Wound Assessment

Table 2. N/A: Did not have this side effect / 1: Mild / 2: Moderate / 3: Severe

A. Blistering	N/A	1	2	3
B. Scarring	N/A	1	2	3
1. Swelling	N/A	1	2	3
2. Redness	N/A	1	2	3
3. Crusting	N/A	1	2	3
4. Pustulation	N/A	1	2	3
5. Scaling or flaking skin (exfoliation)	N/A	1	2	3
6. Erosion (ulceration)	N/A	1	2	3
7. Hyperpigmentation	N/A	1	2	3
9. Hypopigmentation	N/A	1	2	3
10. Urticaria	N/A	1	2	3
11. Infection	N/A	1	2	3
12. Folliculitis/ Acne	N/A	1	2	3
14. Oozing	N/A	1	2	3

--	--

Overall Appearance Scale (blinded MD to complete with photos)

- Physicians will consider both cosmetic appearance but also the degree of photodamage and clinical atypia.

	Co2 treatment site	Co2 + epidermal graft Treatment site	Control site
Excellent	 5	 5	
Good	 4	 4	
Satisfactory	 3	 3	
Poor	 2	 2	
Unacceptable	 1	 1	

End points:

- AK count
- NMSC count
- change in overall clinical appearance
- time to healing

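### The blinded photographic appearance rating is scheduled at Day 3 and Day 7, when the pictures can be expected to show which sites were ablated and which is the untreated control

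*Protocol*

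**What the plan says.** Research Design and Methods names as primary measure (b) a "blinded evaluation of severity from standard digital photographs taken before and after the treatments". The same section lists overall clinical appearance among the other study endpoints.

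The visit schedule has a column headed "Overall Appearance scale". It is marked at baseline, Day 3, Day 7, Week 4, Month 3, Month 6, Year 1 and Year 3, and the photograph column is marked at each of those visits. The form, in the part on assessments by investigators and blinded evaluators, is headed "Overall Appearance Scale (blinded MD to complete with photos"). Its three columns are named for the CO2 site, the CO2 plus graft site and the control site.

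The Day 3 and Day 7 visit description instead lists "Investigator assessments: wound assessment, overall clinical appearance". Evaluation of Safety and Efficacy says "Assessed by investigators (non-blinded) and by blinded evaluators (clinical photographs), periodically for 3 years after a single treatment session". So the visit descriptions place appearance with a person whom the protocol calls non-blinded, and the form places it with a blinded physician.

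**The concern.** Every subject carries all three conditions side by side, so masking depends wholly on whether the image gives the condition away. Shortly after ablation it can be expected to do so. A score given then reflects what the rater knows as well as what the rater sees. It also measures the wrong thing: the scale asks for cosmetic appearance, photodamage and clinical atypia, which an open or crusted wound can hardly show.

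The lesion counts come from examination at the visits, so the photograph rating is the main protection against observer expectation among the clinical efficacy measures. If its masking fails, an appearance advantage for the treated sites could partly be rater expectation.

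**Working it through.** The protocol gives no figure to reproduce. The check compares its sections and counts visits.

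**1. Is a blinded photo rating scheduled on those days?** The schedule marks the scale and the photograph at Day 3 and Day 7, and the form gives that scale to a blinded physician using photographs. Together they schedule it.

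**2. Does the investigator heading in the visit descriptions change that?** The descriptions put overall appearance under investigator assessments at every follow-up visit from Day 3 to Year 3. If that heading meant an open rating, no visit would have a blinded one. That would contradict the form, primary measure (b), Evaluation of Safety and Efficacy, and Data and Safety Monitoring, which gives overall efficacy assessment to blinded investigators. Nothing singles out Day 3 and Day 7 as open. The conflict is real, but it does not remove the problem.

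**3. Can treated be told from control?**
- Under Laser treatment, ablation reaches the base of the epidermis and any remainder is wiped away. Soaks and ointment then go "onto the treated areas for up to 7 days post op as needed", a period that takes in both visits.
- The laser risk table lists redness, swelling, crusting, weeping, erosion and oozing as common.
- In Specific Aims the comparator is "control (no intervention").

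A freshly ablated portion next to intact skin can be expected to be recognisable.

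**4. Can the grafted site be told from the CO2-only site?** The blister roofs are "transferred to a sterile Tegaderm wound dressing that will be applied to the recipient site". No removal time is given, nor any rule on whether the dressing is on when the photograph is taken. Both active sites are laser wounds. Recognition of the graft is therefore an inference.

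**5. How many ratings are affected?**
- By the schedule, the post-treatment ratings are Day 3, Day 7, Week 4, Month 3, Month 6, Year 1 and Year 3, which is 7. Share: 2/7 = 29%.
- The visit descriptions add Years 1.5, 2 and 2.5: 7 + 3 = 10. Share: 2/10 = 20%.
- If redness persists at Week 4 (assumption), the shares become 3/7 = 43% and 3/10 = 30%.

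**6. How far could it spread?** If one reader sees the whole series (assumption), knowledge of the control's location could reach the 7 − 2 = 5 later scheduled ratings in each of the 30 subjects. The protocol has no rule on separate readers, reading order or withheld photographs. If early and late pictures go to different readers, carry-over by this route is nil.

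**7. What would remain?** Without Day 3, Day 7 and Week 4, 4 post-treatment ratings remain by the schedule (Month 3, Month 6, Year 1, Year 3), and 10 − 3 = 7 by the visit descriptions.

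**The case against.** The strongest reply is that the visit description makes Day 3 and Day 7 appearance an open investigator rating, so no mask is broken. Part of this stands: the sections disagree on who rates, and the disagreement is itself a defect. It does not clear the schedule, because the same heading covers every later visit too.

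Three stronger readings are tempting, and the protocol does not support them as fact.
- A reader might infer that the photographs disclose each site's treatment, graft included. Without a dressing-removal time, only treated versus control is supported.
- A reader might infer that all later ratings are contaminated. That assumes one reader sees the series. The protocol speaks of blinded evaluators in the plural and does not say who reads what, or when.
- A reader might infer that the primary measure is biased. The scale is the only photo-rating instrument given, so it is the apparent vehicle for measure (b). But overall clinical appearance is also listed among the other endpoints, and no sentence ties measure (b) to Day 3 or Day 7. Which visits enter an analysis may be settled in an analysis plan not shown here.

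It is also fair to say that removing the early ratings is not enough. The printed form names each site's treatment, so if it is completed as it stands it discloses allocation at every visit.

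**Conclusion.** The point holds in limited form. The schedule and the form together call for a blinded photographic rating at Day 3 and Day 7: 2 of 7 scheduled post-treatment ratings, or 2 of 10 by the visit descriptions. At those visits the rater cannot be considered blinded to treated versus control. This rests on the ordinary expectation that skin ablated through the epidermis looks different from untreated skin 3 and 7 days later, which the protocol's own wound-care period and risk table support.

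Identification of the grafted site, carry-over to later ratings and an effect on primary measure (b) remain possible but are not established. The sections also conflict on who rates appearance and must be reconciled. The change is worth making because it removes an avoidable loss of masking at little cost.

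**What to change.** 1. Reconcile the visit schedule, the visit descriptions, Evaluation of Safety and Efficacy and the form on who rates overall appearance and at which visits, including Years 1.5 to 2.5, which appear in the descriptions but not in the schedule column.
2. Remove the blinded rating at Day 3, Day 7 and Week 4. The investigator's wound assessment is already scheduled at all three. Label any appearance score kept there as unblinded and leave it out of the blinded endpoint.
3. State that the blinded reader receives only baseline and Month 3 or later photographs, in random visit order, and that earlier photographs are withheld from that reader.
4. Replace the treatment-named columns on the form with coded site labels, with the key held away from the reader.

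This changes wording and the form; it adds no visit, photograph or reader. The cost is that there is no masked appearance score in the first weeks. Background and Significance hypothesises that grafting hastens healing, and time to healing is a listed end point, so evidence on early healing, including any graft benefit, would rest on the non-blinded wound form. Masking from Month 3 may still be imperfect, since the protocol lists pigment change among the laser's risks.
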